The adductor canal block of the saphenous nerve is a well-established regional anesthetic technique for knee surgery, and it is recognized for its excellent analgesia with a notable absence of motor involvement, even with continuous perineural local anesthetic infusions. The adductor canal block is known for a high success rate because the adductor canal can be easily visualized with ultrasound at the mid-thigh. While the anatomy of the adductor canal has been elucidated by several imaging and cadaveric studies, factors influencing the spread of local anesthetic during adductor canal nerve block are less well understood. Different volumes of local anesthetic injected

through myriad anatomic approaches produce variable spread. Injectate spread has been shown to span from the femoral triangle to the popliteal fossa with only 15 mL of aqueous volume. One case report notes the apparent partial blockade of the sciatic nerve as a result of a common transsartorial approach to the adductor canal block. Another case report notes motor block of the quadriceps muscle with a midthigh approach to the adductor canal block. Furthermore, one study reports a staggering 67% incidence of motor weakness associated with a bolus of 15 mL of local anesthetic through an adductor canal catheter placed in the midthigh. Additionally, injection pressure has been shown to dramatically influence the spread of lumbar plexus block. Sustained injection pressures > 20 psi during intermittent injection of local anesthetic into the lumbar plexus have been associated with a 60% incidence of bilateral femoral nerve block and a 50% incidence of neuraxial block to the level of T11 or above, compared to no spread in the low injection pressure group (< 15 psi). Injection pressure has not been studied in adductor canal nerve blocks in human clinical trials. We hypothesize that, for a given injectate volume, the pressure during injection will affect local anesthetic spread towards the femoral triangle (cranially) and the popliteal fossa

(caudally). We speculate that high injection pressures will lead to greater spread of local anesthetic during mid-thigh adductor canal nerve blocks.

4) Inclusion and Exclusion Criteria*

Inclusion criteria:

1. Planned general anesthetic.
2. ASA classes I, II, or III.
3. Patients aged 18-65.
4. English-speaking patients.

Exclusion criteria:

1. ASA classes IV and V.
2. Patients younger than 18 or older than 65.

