The patient will be positioned supine, with the ipsilateral thigh and knee prepped in sterile fashion using chlorhexidine/alcohol. A high-frequency ultrasound probe will be covered in a sterile transparent dressing. First a survey scan will be performed at the anteromedial aspect of the mid-thigh, defined as the middle one-third of the distance between the base of the patella and the lower border of the greater trochanter. The probe will be oriented transversely to identify the femoral artery and saphenous nerve in short-axis cross-section, and an image will be recorded. The adductor canal will be scanned in its entirety, with special consideration paid to the femoral triangle just caudad to the inguinal ligament and the popliteal fossa; images will be recorded at both locations. An in-line injection pressure manometer, the Compass CT (Centurion Medical Products, Williamston, MI), will be used to measure injection pressure during adductor canal nerve blocks. A 4 inch, blunt, short beveled needle will be introduced in-plane, in an anterolateral to posteromedial direction, close to the fascial plane between the sartorius and vastus medialis muscles. After negative aspiration, the needle tip location will be confirmed by injection of 0.5 mL of air. Subsequently, an initial bolus of 1 mL of local anesthetic will be administered at < 15 psi in order to decrease risk of intraneurial injection and nerve injury. The remaining 14 mL of ropivacaine 0.5% will thereafter be injected in 5 mL aliquots, maintaining either > 20 psi or < 15 psi based on patient randomization. Injectate spread will be assessed by ultrasound survey after completion of the adductor canal nerve block, where injectate spread is defined as the distance between the uppermost and lowermost limits of spread of local anesthetic as assessed by ultrasound.

Block evaluation will occur 30 minutes after block placement, with motor and sensory testing of both lower extremities as previously mentioned. Additionally, NRS pain ratings will be recorded pre- and post-evaluation. Block success will be determined by testing for pinprick sensation in the saphenous nerve distribution in the ipsilateral lower leg as compared with the contralateral lower leg. Patients who fail to demonstrate block success will be withdrawn from further study.

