Intraoperatively, patients will undergo general anesthesia. General anesthesia will be induced with IV propofol and maintained with sevoflurane or desflurane. Intraoperative fentanyl will be titrated as needed intraoperatively, and the doses will be recorded.

The regimen for postoperative analgesia will consist of oxycodone/acetaminophen 5/325 mg by mouth every 4 hours as needed and hydromorphone 0.5 mg intravenously every hour as needed for breakthrough pain. Doses will be recorded. Postoperative antiemetics will include ondansetron 4 mg intravenously every 8 hours as needed for nausea and/or vomiting, and a single dose of promethazine 12.5 mg intramuscularly if intractable to ondansetron.

Postoperative evaluation will be performed by a research team blinded to injection pressure randomization information. The patient will be assessed in person immediately postoperatively, 30 minutes postoperatively, 1 hour postoperatively, and at the time of discharge. Both sensory and motor testing will be repeated in both lower extremities as previously described, and NRS pain scores will be recorded.

The patient will be evaluated by physical therapy postoperatively using the Lower Extremity Function Scale (LEFS). The LEFS is a self-reporting measure which will be administered during

the initial physical therapy assessment, and will then be administered at weekly intervals for 4 weeks.

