Research subjects will be counseled that their participation in the study is voluntary, and that they may refuse to participate or withdraw from the study at any time without penalty or loss of benefits to which the patients are otherwise entitled. Withdrawal from the study will not affect their medical care they receive from the study doctor or from the University of Miami Hospital. The patient will be counseled that they must tell their study doctor if they wish to stop taking part in the study.

Furthermore, the research subjects' participation in the study may be discontinued without their consent at any time by the study doctor, for instance if the patient has a medical condition which is a contraindication for the procedure, or if a serious, potentially life-threatening complication develops as a result of the procedure. The IRB or regulatory authorities may also discontinue research subjects' participation in the study.

In the case that research subjects are withdrawn from the study, the study staff and the investigator will stop collecting health information; however, they will continue to use the information already collected to evaluate the study results.

Finally, if research subjects start the study and then decide to withdraw, they cannot later continue to participate in the study.

12) **Risks to Subjects***

There are risks normally associated with adductor canal nerve block. These risks are listed below:

UNCOMMON	RARE
Failure of the nerve block to work properly.	Injury to the blocked nerve.
	Excessive bleeding at the site of injection.
	Infection at the site of injection.

	Inadvertent injection of local anesthetics into the bloodstream, causing seizures and/or heart rhythm problems.
--	---

In patients receiving an injection pressure > 20 psi, there is an increased risk of injury to the blocked nerve, such as with intrafascicular injection. To minimize this risk, all injections will be preceded by injection of 1 mL of local anesthetic at an injection pressure < 15 psi, to rule out intrafascicular injection.

13) Potential Benefits to Subjects*

There is no direct benefit to the subjects.

14) Sharing of Results with Subjects*

Results will not be shared with research subjects or their physicians.

15) Setting

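### Withdrawing block failures at 30 minutes leaves opioid use, postoperative pain and LEFS measured only in a subset selected after randomisation

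*Combined protocol and SAP*

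**What the plan says.** Section 8 (Procedures Involved) sets the test and its timing: "Block evaluation will occur 30 minutes after block placement, with motor and sensory testing of both lower extremities". The criterion is that "Block success will be determined by testing for pinprick sensation in the saphenous nerve distribution in the ipsilateral lower leg", compared with the other leg. The consequence of failing it is: "Patients who fail to demonstrate block success will be withdrawn from further study".

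Section 11 (Withdrawal of Subjects) says what withdrawal means for data: "In the case that research subjects are withdrawn from the study, the study staff and the investigator will stop collecting health information". It adds that "they will continue to use the information already collected to evaluate the study results".

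Postoperative follow-up is also set out in Section 8: "The patient will be assessed in person immediately postoperatively, 30 minutes postoperatively, 1 hour postoperatively, and at the time of discharge". LEFS is collected at the first physical therapy assessment and then weekly for 4 weeks. Section 7 (Study Endpoints) names IV opioid use, pain scores and physical therapy milestones as secondary endpoints; Section 2 identifies the milestones as LEFS scores.

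No section defines an analysis population, a missing-data method or follow-up for block failures. Section 9 (Data Management) raises 20 per group to 25 for dropout that is not anticipated. It does not mention this planned withdrawal.

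**The concern.** Randomisation makes the two pressure groups comparable at the moment of injection. The 30-minute test comes after that, and its result may depend on the injection. Dropping failures at that point means the later endpoints compare successes under one pressure with successes under the other, and these need not be the same kind of patient.

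Two things could go wrong if failure rates differ by arm:

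- **Selection.** If patients prone to failure also tend to have more pain, the arm with more failures sheds more of them and looks better than it is.
- **An omitted pathway.** The blocks are given for postoperative analgesia. If pressure changes the chance that the block works, that is one route by which it could change pain and opioid use, and a success-only comparison cannot see it.

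An effect of pressure on saphenous success is plausible, since the hypothesis in Section 3 (Background) is that pressure changes where the anaesthetic goes. The documents do not show such an effect.

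**Working it through.** **Step 1: which endpoints are affected.**

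| Endpoint | When measured | Available for block failures? |
|---|---|---|
| Spread (primary) | Ultrasound survey after the block is completed | Yes, kept under Section 11 |
| Femoral and sciatic block | 30 minutes after the block | Yes, kept under Section 11 |
| IV opioid | During and after surgery | No |
| Postoperative NRS | Four postoperative times | No |
| LEFS | First physical therapy visit, then weekly for 4 weeks | No |

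The repeat postoperative sensory and motor tests are lost as well, although they are not named endpoints.

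**Step 2: inputs for size.** From the documents: 25 patients per group. There is no failure rate to reproduce. Section 12 (Risks to Subjects) puts "Failure of the nerve block to work properly" in its uncommon column, and Section 3 says "The adductor canal block is known for a high success rate". Everything else is assumed: failure rates of 2% to 20%, failure-prone patients scoring d = 1 or 2 NRS points worse in either arm, and an NRS SD of 2 to 3.

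**Step 3: spurious difference when pressure has no effect on pain.** Let pH and pL be the failure proportions in the higher- and lower-failure arms. A share pH of patients is failure-prone. All of them fail in the first arm, and a nested share pL fails in the second. Among successes, the first arm has no failure-prone patients and the second has (pH − pL)/(1 − pL). So

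spurious difference = d × (pH − pL)/(1 − pL), while the difference among all randomised patients is 0.

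| Failure, pH vs pL | (pH − pL)/(1 − pL) | d = 1 | d = 2 |
|---|---|---|---|
| 5% vs 5% | 0 | 0 | 0 |
| 5% vs 2% | 0.03/0.98 | 0.031 | 0.061 |
| 10% vs 5% | 0.05/0.95 | 0.053 | 0.105 |
| 20% vs 5% | 0.15/0.95 | 0.158 | 0.316 |

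The difference favours the arm with more failures. A simulation of the same model agreed to within 0.001.

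**Step 4: a different model.** Suppose instead that prognosis and block success share a latent correlation of 0.3 to 0.5. The spurious difference is then 0.03 to 0.04 SD at 10% vs 5%, 0.07 to 0.12 SD at 20% vs 5%, and zero at equal failure.

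**Step 5: comparison with sampling error.** SE = SD × √(2/25) = 2 × 0.283 = 0.57 to 3 × 0.283 = 0.85 NRS points. Every value in Step 3 is below one SE. So is every value in Step 4, where the SE is 0.283 in SD units.

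**Step 6: the omitted pathway.** If a failed block itself adds d points, the pressure effect left out of a success-only comparison is d × (pH − pL): 0.05 to 0.10 points at 10% vs 5%, and 0.15 to 0.30 at 20% vs 5%.

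**Step 7: how many patients.** Expected failures per 25 are 0.5 at 2%, 1.25 at 5%, 2.5 at 10% and 5 at 20%. At 5% in both arms, the chance of at least one failure among 50 is 1 − 0.95^50 = 92%.

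**The case against.** The strongest objection is size. At failure rates that fit the protocol's own description of failure as uncommon, the spurious difference is at most about 0.11 points. With an SE of 0.57 that is a shift of 0.105/0.566 = 0.19 SE, which moves a two-sided 5% test to about 5.4%. At 20% vs 5% with d = 2 and SD 2, and with the SE recomputed for 20 and 23.75 successes (0.61), the rate reaches about 8%; that failure rate is hard to square with an uncommon event. The Step 3 model is also close to worst case, because every failure-prone patient fails in one arm. All of this stands, and it limits how serious the point can be.

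Second, differential failure is an inference. The hypothesis concerns spread up and down the thigh, whereas success is tested in the saphenous distribution, and both arms receive the same volume under ultrasound. This stands too; the point rests on what may happen.

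Third, opioid doses would probably sit in the clinical record, to which Section 9 gives the investigators access. This does not rescue the data, because Section 11 stops study staff from collecting them after withdrawal. It would not supply LEFS or the scheduled pain ratings in any case.

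Fourth, a success-only comparison answers a legitimate question about blocks that work. It does, but the protocol does not say that this is its aim, and the comparison remains available if everyone is followed.

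Finally, Section 8 gives no pinprick score that counts as success. That affects how failure is reported by arm, but not whether patients should be kept.

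**Conclusion.** The point holds. As written, three named secondary endpoints (IV opioid use, postoperative pain and LEFS) would be observed only in a subset defined after randomisation, and no rule elsewhere in the protocol compensates. The primary endpoint and the 30-minute femoral and sciatic results are not affected.

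The likely bias is small: 0.03 to 0.11 NRS points for failure rates of 10% or less, up to 0.32 at 20% versus 5%, and below one standard error throughout. These figures rest on assumed failure rates, an assumed 1 to 2 point penalty and an assumed SD. If the arms fail equally often and the same kind of patient fails, the bias is near zero. The case for acting is that the size cannot be known in advance, the data will not exist to check it afterwards, and the correction is cheap. It should be fixed, but it does not threaten the main result.

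**What to change.** In Section 8, replace the withdrawal sentence with:

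> *Patients without saphenous block at 30 minutes are recorded as block failures, remain in the study, complete all later scheduled assessments and are analysed in their randomised group.*

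Report block failure by arm, and keep the success-only comparison as a labelled sensitivity analysis.

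In Section 11, add only:

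> *Block failure at 30 minutes is not a withdrawal and does not stop data collection.*

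The existing rule stays as it is for withdrawal of consent and for discontinuation by the study doctor, the IRB or regulatory authorities.

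The cost is two sentences, plus assessments already on the schedule for about 1 to 3 more patients per group at 5% to 10% failure (1.25 to 2.5 expected). The downside is that pain and opioid data become somewhat more variable, because failed blocks and whatever care those patients receive are included. The change concerns follow-up and analysis only and alters no treatment.

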NCT02563990

PROTOCOL TITLE:

INJECTION PRESSURE AND ADDUCTOR CANAL BLOCK

V2 7/10/2015

1) Protocol Title

Impact of Injection Pressure on the Spread of Local Anesthetic During Adductor Canal Nerve Block

Authors: [name], [name], [name], [name], DNP, [name], [name], [name], [name]
Department of Anesthesiology, University of Miami, Florida

Brief description: This is a prospective, randomized, single-blinded human clinical trial that will examine how injection pressure influences the spread of a given volume of injectate in the adductor canal, during adductor canal nerve block. Our study population will be patients undergoing elective anterior cruciate ligament repair in the distal lower extremity and receiving preoperative adductor canal nerve blocks for postoperative analgesia. They will be randomized into two groups of 25 patients each. We speculate that high injection pressures (>20 psi) will lead to greater spread of local anesthetic than low injection pressures (<15 psi) during mid-thigh adductor canal nerve blocks. Our primary endpoint is the spread of injectate, defined as the distance between the uppermost and lowermost limits of spread of local anesthetic as assessed by ultrasound. Our secondary endpoints are the incidence of femoral and sciatic nerve blocks 30 minutes after block placement, amount of IV opioid administered intraoperatively and postoperatively, postoperative pain (Numeric Rating Scale, 0-10), and postoperative physical therapy milestone achievement.

2) Objectives*

The purpose of this study is to evaluate the impact of injection pressure on the spread of local anesthetic in the adductor canal during an adductor canal nerve block. Our primary endpoint is the spread of injectate, defined as the distance between the uppermost and lowermost limits of spread of local anesthetic as assessed by ultrasound. Our secondary endpoints are the incidence of femoral and sciatic nerve blocks 30 minutes after block placement, amount of IV opioid administered intraoperatively and postoperatively, preoperative and postoperative pain (Numeric Rating Scale, 0-10), and postoperative physical therapy milestone achievement, namely Lower Extremity Function Scale (LEFS) scores.

3) Background*

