This will be a randomized, single-blinded controlled trial in patients undergoing elective, anterior cruciate ligament repair in the distal lower extremity at the ambulatory surgery suite at the University of Miami Hospital. Cohort-matched (ASA status, BMI range, age, height, weight) patients will be randomly assigned via a method of predetermined randomization via assigned numbers to a low injection pressure group (injection pressure < 15 psi) and a high injection pressure group (injection pressure > 20 psi). Patients will receive preoperative adductor canal blocks for postoperative analgesia, and will undergo general anesthesia intraoperatively.

Patients will be assessed preoperatively in a designated presurgical area at UMH and the Lennar Foundation Medical Center. After undergoing an initial history and physical, the patient will rate his or her pain in the operative extremity on the Numeric Rating Scale. The patient will subsequently undergo sensory and motor testing of both lower extremities. Sensory testing will use a pinprick method in the femoral (anterior thigh), saphenous (medial calf proximal to the medial malleolus, top of the patella) and sciatic (posterior lateral calf, plantar surface of the foot) nerve distributions, with a score of 2 indicating "sharp", 1 indicating "dull", and 0 indicating "unable to feel the stimulus". The control limb for pinprick testing will be the contralateral lower extremity. Motor testing will evaluate the femoral and sciatic nerves of each lower extremity by assessing strength of knee extension, and plantarflexion and dorsiflexion of the ankle, respectively, against resistance. The patient will be assessed for motor function in the seated position on an examination table with both legs dangling passively. A score of 3 will indicate full power, 2 mild weakness, 1 moderate weakness, and 0 a complete absence of power. After testing is completed, a subsequent NRS pain rating will be recorded.

Blocks will be performed preoperatively, with standard ASA monitors (electrocardiography, noninvasive blood pressure at least every 5 minutes, pulse oximetry, and qualitative capnography). Blocks will be performed under conscious sedation (midazolam 0.05-0.08 mcg/kg IV and fentanyl 0.5-2 mcg/kg IV) if necessary, but the ability to interact with the anesthesiology team will be preserved.

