Our research team will conduct our procedures and evaluation in the University of Miami ambulatory surgery suite. We will follow-up with patient postoperative progress telephonically on a weekly basis with the use of a self-reporting physical therapy questionnaire known as the Lower Extremity Function Scale (LEFS).

16) Resources Available

The facilities at the ambulatory surgery suite at the University of Miami Hospital and The Lennar Foundation Medical center are sufficient for adequate assessment, monitoring, and execution of study-related procedures. There is a designated pre-surgical holding area with blood pressure, ECG, and pulse oximetry monitoring as well as a continuous source of oxygen in order to conduct the procedure according to the standard of care. There is adequate nursing and ancillary staff to facilitate all study-related perioperative procedures. An ultrasound adequate for conducting the procedure is available at all times, as well as an emergency cart containing emergency drugs and equipment in the case of a serious, possibly life-threatening emergency.

All research staff conducting procedures will be licensed physicians clinically trained in anesthesiology and procedure technique will be standardized. Clinical evaluation will be

performed by licensed physicians or nurse practitioners. Physical therapy will be conducted by licensed physical therapists and physical therapy milestones will be standardized.

Recruitment of potential research subjects will be straightforward. The volume of anterior cruciate ligament surgeries is sufficient to expect a recruitment period of 3-6 months, even if as few as 25% of potential research subjects actually agree to participate in the study.

The amount of time we intend to devote to conducting and completing the research is 6-12 months.

17) Recruitment Methods

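### The Lower Extremity Function Scale (LEFS) schedule is not fixed relative to surgery and has no pre-operative value, so same-week scores can come from different recovery days and baseline adjustment is impossible.

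*Combined protocol and SAP*

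**What the plan says.** Section 2 names the functional secondary endpoint as "postoperative physical therapy milestone achievement, namely Lower Extremity Function Scale (LEFS) scores". Sections 1 and 7 list milestone achievement without naming the scale.

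Section 8 has the LEFS, a self-report form, given after surgery during "the initial physical therapy assessment, and will then be administered at weekly intervals for 4 weeks". Section 15 adds the mode of follow-up: "We will follow-up with patient postoperative progress telephonically on a weekly basis", using the LEFS. Section 16 says that "physical therapy milestones will be standardized", but not when the first visit takes place.

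The pre-operative work-up in section 8 is a history and physical, then "the patient will rate his or her pain in the operative extremity on the Numeric Rating Scale", then "The patient will subsequently undergo sensory and motor testing of both lower extremities". The LEFS is not part of it. Sections 2 and 7 list pain both before and after surgery, but physical therapy milestones only after it.

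No section names a main LEFS time point, a change score, or an adjustment for baseline or for days since surgery.

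**The concern.** Pain, sensory and motor assessments each have a pre-block value and defined times: 30 minutes after the block, then immediately, 30 minutes and 1 hour after surgery, and at discharge. The LEFS is the only repeated patient assessment with neither a baseline nor a time fixed relative to surgery.

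Two things are at stake.

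- **Timing.** The LEFS clock starts at an event that follows randomization and has no stated date. If first visits fall on different days, a given week number covers a range of recovery days while function is presumably improving. If the mean first-visit day also differs between pressure groups, the comparison mixes recovery day with arm, and randomization does not protect against that.
- **Baseline.** Without a pre-operative score, variation in starting function stays in the residual, and a chance imbalance between arms of 25 cannot be adjusted away. The matching factors in section 8 (ASA status, BMI range, age, height, weight) do not include function.

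**Working it through.** **Figures in the plan.** There is no LEFS figure to reproduce. The power statement in section 9 (20 per group, 25 enrolled) concerns motor weakness. From the documents I take only 25 per arm, two-sided 0.05 and 80% power. All other inputs below are assumptions.

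**Assumed inputs.** LEFS rises 4 to 8 points per week early after surgery; first-visit day has an SD of 3 to 7 days within each arm; LEFS has a within-arm SD of 12 points at a fixed recovery day; the correlation between pre-operative and later LEFS is 0.3 to 0.5.

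**1. Noise from timing.** If first-visit day is unrelated to function at a fixed day:

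- Added SD = slope per week × (SD in days / 7)
- Low: 4 × 3/7 = 1.7 points. High: 8 × 7/7 = 8.0 points.
- Variance inflation = added SD² / 12². Low: 1.714²/144 = 2%. High: 64/144 = 44%.
- Standard error multiplier: √1.02 = 1.01 to √1.44 = 1.20.
- If all first visits are on the day of surgery, the first-visit SD is 0 and so is this term.

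**2. Bias if timing differs by arm.** Bias = slope per week × (difference in mean start day / 7). For an illustrative 3-day difference: 4 × 3/7 = 1.7 to 8 × 3/7 = 3.4 points, or 0.14 to 0.29 SD. If the arms have the same mean start day, this is zero.

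**3. Precision at 25 per arm.**

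- Detectable difference, no baseline and no timing spread: (1.960 + 0.842) × √(2/25) = 0.79 SD, or about 9.5 points.
- With the timing inflation in step 1: 9.5 × 1.01 = 9.6 to 9.5 × 1.20 = 11.4 points.
- Adjusting for a pre-operative score (no timing spread) removes a fraction r² of the residual variance: 0.3² = 9% to 0.5² = 25%. The detectable difference becomes 0.79 × √0.91 = 0.76 SD to 0.79 × √0.75 = 0.69 SD.

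**4. Chance imbalance in starting function.** The standard error of the baseline difference is √(2/25) = 0.28 SD. The probability of an imbalance above 0.5 SD in either direction is about 8%.

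**5. Timing noise after the fix.** If calls are spread evenly over a window of plus or minus 2 days, the timing SD is 4/√12 = 1.15 days. The added SD is 4 × 1.15/7 = 0.66 to 8 × 1.15/7 = 1.3 points, so variance inflation is 0.66²/144 = 0.3% to 1.3²/144 = 1.2%.

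**The case against.** The strongest reply is that the first assessment may be on the day of surgery. Section 8 describes it straight after the recovery-room assessments, and section 15 places the team's procedures and evaluation in the ambulatory surgery suite before the weekly calls begin. On that reading all patients share one clock, the calls fall near days 7, 14, 21 and 28, and the timing problem nearly disappears. This is a fair reading but not a certain one. It stands as a reason not to claim that dates do vary, and it does not supply the missing day.

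Three further objections stand in part.

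- A reader might infer that late starters are slow recoverers who are scored later and look better, so that a true difference is hidden. The documents do not support this. They say nothing about what determines the visit date, and nothing links injection pressure to it. Masking between arms would need such a link.
- A reader might infer that the missing baseline biases the comparison. It does not: randomization balances starting function in expectation. Nor would a holding-area LEFS recover function before the injury, because it measures the injured knee.
- A reader might infer that a same-day first score would sit at the bottom of the scale. The documents give no LEFS values, so this cannot be shown.

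It is also true that every magnitude here rests on assumed inputs, and that the low end of the timing range is trivial.

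**Conclusion.** Both textual facts hold: no LEFS is tied to days since surgery, and none is collected before surgery. The plan therefore permits same-week scores from different recovery days; it does not establish that they will occur. The consequence ranges from almost nothing (all first visits on the day of surgery), through a variance increase of 2% to 44% (dates vary alike in both arms), to a bias of 1.7 to 3.4 points for each 3 days by which mean start day differs between arms. The missing baseline forgoes a 9% to 25% cut in residual variance. These sizes rest on the assumed slope, spread, SD and correlation.

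The point is limited to one secondary endpoint. Injectate spread, the primary endpoint, and the stated sample size do not depend on it. It is worth acting on because the remedy is cheap and a pre-operative score cannot be collected after surgery.

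**What to change.** In section 8, replace the LEFS schedule with wording such as: *The LEFS is completed once in the holding area, after consent and before sedation and block, and then by telephone on days 7, 14, 21 and 28 after surgery (window plus or minus 2 days), whatever the date of physical therapy.* Align section 15 with these days. Add an analysis sentence: *Arms are compared on LEFS adjusted for the pre-operative score.*

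If the sponsor already intends every first assessment to be on the day of surgery, saying so would close most of the timing gap, but the baseline would still be missing.

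The cost is one short form and a few minutes per patient at a visit where patients are already interviewed and tested. The weekly calls are already planned. No treatment or clinical rule changes. Which LEFS day is the main one, and how milestone achievement is worded in sections 1 and 7, are separate choices for the sponsor.
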